clinically meaningful and consistent with previous trials of renal denervation in a similar population¹. An observed difference between groups of 5 mmHg with an observed SD as high as 11.2 mmHg per group would be considered statistically significant at a two-sided alpha level of 0.05.

Endpoints and Planned Statistical Analysis

The following populations are defined for analysis:

The Intent-to-Treat (ITT) Analysis Set will include all subjects who were randomized regardless of whether treatment was received. Subjects will be analyzed according to their randomized treatment group, irrespective of treatment received.

The Safety Analysis Set will include all subjects who received treatment. Subjects will be analyzed according to the actual treatment received, irrespective of treatment assignment.

The Per-Protocol (PP) Analysis Set will include subjects with no important protocol deviations. Subjects will be analyzed according to the actual treatment received.

Primary efficacy endpoint

The primary efficacy endpoint is defined as the change in mean 24-hour ambulatory SBP from baseline to 8 weeks post-treatment. This will be summarized and compared between the 2 treatment groups using the independent two-sample t-test.

Secondary efficacy endpoints:

- Change in mean 24-hour, daytime, (07:00 to 21:59), and nighttime (22:00 to 06:59) ambulatory SBP and DBP from baseline to time points post-treatment.
- Change in mean office SBP and DBP from baseline to time points post-treatment.
- Percentage of subjects controlled to target blood pressure values.
- Use of antihypertensive medication(s) from time of procedure to 8 weeks post-treatment (emergency use medication).
- Use of antihypertensive medication(s) (including increases/decreases) from 8 weeks to 6 months and 1-year post-treatment (titrated according to standardized formula to maintain a target SBP of <140 mmHg and ≥90 mmHg).
- Compliance with not taking antihypertensive medications through 8 weeks post-treatment.

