- 11 If the renal duplex ultrasound assessment at 6 months cannot be performed, or if the results are non-diagnostic, CTA/MRA/renal angiography may be performed if agreed with the sponsor (depending upon local regulatory approvals and site capacity). If renal artery stenosis of >60% or any other significant abnormality is suspected or confirmed by renal duplex ultrasound, as evaluated by the core laboratory, or as the result of other clinical assessments, those findings should be confirmed using the imaging modality used at screening (CTA/MRA/renal angiography). The choice of imaging may be changed at the discretion of the investigator and should be discussed with the sponsor.
- 12 Subjects with an eGFR of >45 and <60 mL/min/1.73 m² based on the screening serum creatinine sample will undergo blood sampling for post-contrast serum creatinine measurement 48-96 hours after imaging at screening. Subjects with an eGFR of >45 and <60 mL/min/1.73 m² based on the Week -1 (baseline) serum creatinine sample will undergo blood sampling for post-contrast serum creatinine measurement 48-96 hours after imaging during the procedure and any subsequent procedure where imaging contrast is used.
- 13 See Table 3 for details of blood and urine parameters. Tests to be done in the case of ET will be as for the Month 6 visit, but excluding compliance tests.
- 14 For measurement of serum creatinine only (all subjects). This sample must be taken prior to imaging at screening, because the eGFR value based on this measurement will be used to assess whether the subject is excluded or may proceed to have the screening imaging assessment.
- 15 Activated coagulation time (ACT) only is performed on Day 0, per the hospital's standard of care.
- 16 For compliance testing only.
- 17 No antihypertensive medications are permitted from the start of the run-in period until the subject has completed the visit at 8 weeks post-treatment (except in the case of emergencies).
- 18 Antihypertensive medications may be given after the 8-week visit if necessary (according to pre-defined criteria and proposed titration schedule).

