- 3 Subjects with an eGFR of >45 and <60 mL/min/1.73 m² based on the Week -1 (baseline) serum creatinine sample will undergo blood sampling for post-contrast serum creatinine measurement 48-96 hours after imaging during the procedure and any subsequent procedure where imaging contrast is used.
- 4 eGFR will be calculated using the Chronic Kidney Disease Epidemiology Collaboration (CKD-EPI) equation. For all subjects, if the calculated eGFR is reduced >25% from baseline (Week -1), the investigator should repeat the serum creatinine test as soon as possible, but no later than 1 week after the first test. If the repeated calculated eGFR remains >25% from baseline, the investigator should refer the subject for further renal functions evaluations, including review by a nephrologist. Similarly, if a subject's eGFR drops to ≤45 mL/min/1.73 m², then he/she will have renal function monitored and managed by a nephrologist as an additional safety measure following this event and until the event is resolved. In either case, the decrease in eGFR will be reported as an AE.
- 5 Only calculated for those subjects who have serum creatinine measured at this time point.
- 6 Performed per the hospital's standard of care and analyzed at site.
- 7 Compliance testing in relation to antihypertensive medications.

Table 4 Schedule of Blood and Urine Sample Collection (Crossover Phase)

[figure not shown]
Period		Re-Screening Period	Treatment	Follow-Up Period		
Visit Time Point		Up to Wk -4	D 0	D 2 to D 4 (48-96 h) ¹	Wk 4	Mth 6
Visit Window					+/-7 D	+/-4 Wk
Serum chemistry	Sodium	X			X	X
	Potassium	X			X	X
	Serum chloride	X			X	X
	BUN/urea	X			X	X
	Uric acid	X			X	X
	Cystatin C	X			X	X
	Glucose	X			X	X
	Serum creatinine	X		X ²	X	X
	eGFR ³	X		X ⁴	X	X
Liver panel	AST (SGOT)	X			X	X
	ALT (SGPT)	X			X	X
	Alk phos	X			X	X
	Bilirubin (conj)	X			X	X
	Bilirubin (total)	X			X	X
	LDH	X			X	X
	Albumin	X			X	X
	Total protein	X			X	X
Hematology	RBC	X			X	X
	WBC (total and differential)	X			X	X
	HGB	X			X	X
	HCT	X			X	X
	Platelets	X			X	X

Period		Re-Screening Period	Treatment	Follow-Up Period		
Visit Time Point		Up to Wk -4	D 0	D 2 to D 4 (48-96 h) ¹	Wk 4	Mth 6
Visit Window					+/-7 D	+/-4 Wk
Coagulation	aPTT	X				
	PT	X				
	INR	X				
	ACT ⁵		X			
Urinalysis	Specific gravity	X			X	X
	pH	X			X	X
	Glucose	X			X	X
	Ketones	X			X	X
	Protein (total)	X			X	X
	Bilirubin	X			X	X
	Hemoglobin	X			X	X
	Nitrite	X			X	X
	WBC	X			X	X
	RBC	X			X	X
	Bacteria	X			X	X
	Crystals	X			X	X
	Casts	X			X	X

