3.4.2. Secondary Efficacy Endpoints

Secondary efficacy endpoints include:

- Change in mean 24-hour ambulatory diastolic blood pressure (DBP) from baseline to 8 weeks
- Change in mean 24-hour ambulatory SBP and DBP from baseline to 6 months and 1 year
- Change in mean daytime (07:00 to 21:59) ambulatory SBP and DBP from baseline to 8 weeks, 6 months, and 1 year
- Change in mean nighttime (22:00 to 6:59) ambulatory SBP and DBP from baseline to 8 weeks, 6 months, and 1 year
- Change in mean office SBP and DBP from baseline to 8 weeks, 6 months, 1 year, and 2 years
- Percentage of subjects controlled to target blood pressure values.
- Use of antihypertensive medication(s) from time of procedure to 8 weeks post-treatment (emergency use medication).
- Use of antihypertensive medication(s) (including increases/decreases) from 8 weeks to 6 months post-treatment (titrated according to standardized formula to maintain a target office SBP of <140 mmHg and ≥90 mmHg, see Section 7.2.2 of the protocol for more detail regarding medication titration).
- Compliance with not taking antihypertensive medications, as assessed by blood and urine testing, through 8 weeks post-treatment.

3.4.3. Secondary Safety Endpoints Secondary safety endpoints include:

- Major adverse events (MAEs) through 30 days post-treatment, as adjudicated by the Clinical Events Committee (CEC). A MAE is defined as any of the following:
 - o All-cause death
 - o End-stage renal disease (ESRD) (eGFR <15 mL/min/1.73 m² or need for renal replacement therapy)
 - Significant embolic event resulting in end-organ damage or requiring intervention to prevent it
 - Major vascular complications, including major renal artery dissection, renal artery aneurysm or pseudoaneurysm that required intervention or led to renal artery stenosis (>60% diameter stenosis)
 - o Major bleeding related to renal denervation within the renal arteries, or related to the Peregrine Catheter when in the body (per protocol bleeding definition)
 - Significant acute (post-procedural) renal artery stenosis (>60% diameter stenosis) as indicated by the renal angiogram post renal denervation, and confirmed by the angiography core laboratory, which led to one of the following: (i) acute kidney injury per modified Risk, Injury, Failure, Loss of kidney function, and End-stage kidney disease (RIFLE) definition, as confirmed by renal function blood test, or (ii) percutaneous intervention.
 - Hypertensive crisis (hypertensive emergency only)

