5.4.1. Primary Efficacy Endpoint

The mean change in 24-hour ambulatory SBP from baseline to 8 weeks post-treatment will be presented in each group. The difference between groups will be summarized and compared using ANCOVA with adjustment for the baseline 24-hour ambulatory SBP.

The protocol defined window for the 8-week (56 day) visit is ± 7 days. For the purposes of analysis, measurements obtained within -15 days or ± 30 days (i.e., between 41 and 86 days) will be considered valid and will be analyzed as part of the primary endpoint analysis, provided that the subject remained off antihypertensive medication prior to collection of ABPM.

For the primary analysis, all available data will be used. There will be no imputation of data at 8 weeks. This analysis will be repeated in the PP analysis set.

In addition to the primary analysis, the following secondary and sensitivity analyses will be conducted:

- 1. Subjects who meet the protocol defined criteria for antihypertensive drug treatment and receive treatment within the 8 weeks prior to assessment of the primary endpoint will have their 8-week value imputed with their baseline value of ABPM.
- 2. Subjects who meet the protocol defined criteria for antihypertensive drug treatment and receive treatment within 8 weeks will be removed from the analysis.
- 3. Subjects who receive antihypertensive treatment within 8 weeks for any reason or in whom antihypertensive medications are detected via compliance samples will be removed from the analysis.
- 4. Missing data at 8 weeks will be imputed via multiple imputation techniques. The following covariates will be considered for the imputation: treatment group, age, gender, history of diabetes, BMI, anatomy defined by length from ostium to bifurcation, number of medications at baseline, baseline office systolic pressure, 8-week office systolic pressure, baseline 24-hour ambulatory SBP. These factors were chosen based on clinical experience and recent literature (Fengler, 2016) (Id, 2016) (Kandzari, 2015).
- 5. Missing data at 8 weeks and data for those subjects who meet the protocol defined criteria for antihypertensive drug treatment and receive treatment within 8 weeks will be imputed via multiple imputation techniques.

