6 (if needed)	Spironolactone or beta-blocker or clonidine	6
7 (if needed)	Spironolactone or beta-blocker or clonidine	7
8 (if needed)	Spironolactone or beta-blocker or clonidine	8

Abbreviations: ACE = angiotensin-converting enzyme; ARB = angiotensin receptor blocker; BP = blood pressure; CCB = calcium channel blocker; SBP = systolic blood pressure.

- 1. There will usually be 2 to 3 weeks between steps. If the target is reached, there are no further steps even if BP fluctuates above the target. If initial systolic blood pressure (SBP) is ≥160 mmHg, Steps 1 and 2 can be combined. Fixed-combination drug products can be used to decrease pill burden.
- 2. The treatment score will be used for the purpose of the statistical analysis.

Source: Weber et al. 2015

5.5.2.5. Use of Antihypertensive Medication(s) (including Increases/Decreases) from 8 weeks to 6 months Post-Treatment (Titrated According to Standardized Formula to Maintain a Target SBP of <140 mmHg and ≥90 mmHg).

The mean change in the number of antihypertensive medications will be summarized as described in Section 5.7 along with 95% CIs for the mean change in number of medications. The addition of new antihypertensive drugs will be considered an intensification of the antihypertensive regimen. Discontinuation of one or more of the baseline antihypertensive medications without an increase in dose of remaining drugs or addition of new drugs will be considered a reduction in antihypertensive drug regimen.

The mean treatment score will be reported by treatment group and the groups compared via Fisher's Exact test. These analyses will be conducted in the ITT and PP analysis sets.

5.5.2.6. Compliance with Not Taking Antihypertensive Medications Through 8 weeks Post-Treatment. The number and percent of patients in whom no antihypertensive medications are detected according to urine compliance results will be summarized by treatment group and compared using Fisher's Exact test. Subjects who meet the protocol defined criteria for antihypertensive drug treatment and receive treatment within 8 weeks will be excluded from the analysis. These analyses will be conducted in the ITT and PP analysis sets.

5.5.2.7. Use of Antihypertensive Medication(s) according to Defined Daily Dose.

In addition to the protocol specified analyses as described above, prescribed medications will be summarized according to the sum of the defined daily dose (DDD) in order to assess and

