6. CHANGES TO ANALYSES PLANNED IN THE PROTOCOL

There are no changes to the planned analyses in the protocol.

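### The 8-week drug-abstinence endpoint is defined on blood and urine tests but counted on urine alone, so a subject positive only in blood would be reported as compliant

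*SAP*

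**What the plan says.** The protocol synopsis lists the endpoint without naming a test: "Compliance with not taking antihypertensive medications through 8 weeks post-treatment". SAP 3.4.2 names both: "Compliance with not taking antihypertensive medications, as assessed by blood and urine testing, through 8 weeks post-treatment".

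Protocol Table 3 has separate compliance rows for a urine test and a blood test, each marked at Week -1, Week 4, Week 8 and Month 6. Footnote 7 gives their purpose: "Compliance testing in relation to antihypertensive medications". In protocol Table 1 the Week 4 blood sample and the Week 4 urine sample carry the same footnote, 16: "For compliance testing only".

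SAP 5.5.2.6 then sets the analysis: "The number and percent of patients in whom no antihypertensive medications are detected according to urine compliance results will be summarized by treatment group". The arms are compared by Fisher's exact test in the ITT and PP sets. The section makes one exclusion: "Subjects who meet the protocol defined criteria for antihypertensive drug treatment and receive treatment within 8 weeks will be excluded from the analysis".

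SAP 5.4.1, sensitivity analysis 3, also uses the compliance results. It removes subjects treated within 8 weeks for whatever reason, and those "in whom antihypertensive medications are detected via compliance samples will be removed from the analysis".

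SAP Section 6 states: "There are no changes to the planned analyses in the protocol". The change history in Section 7 has no entry that restricts compliance testing to urine.

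**The concern.** The definition uses two matrices and the counting rule uses one. Blood is drawn at Week 4 for no purpose other than compliance testing, and the rule gives that result no role.

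Abstinence is the premise of an off-medication trial, and the compliance table is the objective evidence a reader will use to judge whether the premise held. If part of the detected drug use does not reach that table, the 8-week comparison looks cleaner than it was. One subject could also appear as drug-free in one output and as drug-positive in another, with nothing in the SAP to explain the difference.

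**Working it through.** The plan states no figure for this point, so there is none to reproduce. The check is a reading of the rule, followed by an illustration of size.

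**1. Classification under the text as written**

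| Urine | Blood | SAP 5.5.2.6 (urine only) | SAP 3.4.2 definition (both tests) | Sensitivity analysis 3 (any compliance sample) |
|---|---|---|---|---|
| negative | negative | compliant | compliant | kept |
| positive | negative | not compliant | not compliant | removed |
| positive | positive | not compliant | not compliant | removed |
| negative | positive | **compliant** | not compliant | removed |

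Only the last row differs. The one exclusion in 5.5.2.6 covers subjects who met the rescue criteria and were treated, so it does not catch this row. The last column reads compliance samples as including blood. That is an inference from Table 3 and SAP 3.4.2, because sensitivity analysis 3 names no matrix.

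**2. Direction.** Let u be the share positive in urine and b the share positive only in blood.

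- Compliant share, urine only: 1 − u
- Compliant share, either matrix: 1 − u − b
- Difference: b, which cannot be negative

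The urine-only rule therefore never understates compliance relative to the two-matrix definition.

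**3. Size.** The documents give no value for b. I assume 0 to 8%. SAP 5.5.2.6 uses the ITT set, planned at about 90 subjects (45 per arm).

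- b = 0: 0 × 90 = 0 subjects
- b = 2%: 0.02 × 90 = 1.8 subjects
- b = 8%: 0.08 × 90 = 7.2 subjects

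These counts are before rescue-treated subjects are excluded. The figure of 80 evaluable subjects belongs to the primary endpoint and is not the denominator here.

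**4. Effect on the between-arm comparison.** Fisher's exact test, 45 per arm, with 4 urine-positive subjects in each arm (assumed), gives p = 1.00. Adding blood-only positives to one arm alone gives:

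| Added in one arm | Non-compliant | p |
|---|---|---|
| 2 | 4 v 6 | 0.74 |
| 5 | 4 v 9 | 0.23 |
| 7 | 4 v 11 | 0.09 |
| 9 | 4 v 13 | 0.03 |

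So even the top of the assumed range, placed entirely in one arm, does not reach 0.05 from this starting point. The result depends on that starting point. With no urine positives in either arm, 7 in one arm gives p = 2 × C(45,7)/C(90,7) = 2 × 45,379,620/7,471,375,560 = 0.012. If blood-only positives are split evenly between the arms, the comparison hardly moves.

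**The case against.** The strongest reply is that this is a wording mismatch in one supportive table. The endpoint is secondary, the SAP declares no formal hypothesis testing, and drug use is dealt with elsewhere where it bears on blood pressure. Sensitivity analysis 3 removes treated or drug-positive subjects and is repeated for daytime, nighttime and office systolic pressure. The PP set excludes subjects treated before the primary ambulatory measurement. The extended 8-week window requires the subject to be off medication. All of this stands, and it limits the consequence.

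A reader might infer that the urine-only rule biases the primary endpoint. The documents do not support that. Undisclosed drug use, if unbalanced, could bias the comparison, but a tabulation rule changes neither drug intake, nor who enters the primary ANCOVA, nor the estimate. It can only make such use harder to see.

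A reader might also infer that the two outputs are certain to conflict. They would do so only if a blood-only positive occurs and if compliance samples include blood. The first is not shown in the documents and the second is inferred. The two analyses also serve different purposes and already differ in whom they exclude.

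The table shells and the protocol body are not available here, and a stray 1 in the title of Table 14.2.10 may mark a footnote that covers this. A footnote would not cure contradictory text in the SAP body. Nor is this a departure from the protocol text available, whose endpoint names no matrix; the inconsistency lies within the SAP. Amending SAP 3.4.2 to urine only, with a reason, would also reconcile the text, but it would discard blood results already collected for this purpose.

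**Conclusion.** The point holds as an error in the analysis rule. SAP 5.5.2.6 does not implement the endpoint defined in SAP 3.4.2, and no available text reconciles them. Because the rule says which results to use, and leaves one matrix out, this is more than a missing detail.

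Reported compliance is unchanged or overstated by the blood-only positive share. That share is unknown and is zero if the two matrices always agree. The range of 0 to about 7 subjects rests entirely on the assumed 0 to 8%. The reach is one supportive secondary endpoint and the visibility of hidden drug use; the primary estimate is untouched. Given the low cost of correction, the rule should be corrected before results by arm are seen.

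**What to change.** Rewrite the rule in SAP 5.5.2.6 as follows:

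- A subject is compliant only if no antihypertensive drug is detected in either blood or urine at both Week 4 and Week 8.
- Any positive result in either matrix at either visit makes the subject non-compliant.
- Subjects with a missing sample and no positive result are reported as a separate category, not as compliant. The present text does not say how missing samples, or the two visits, are handled.

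Use the same detection flag for the compliance-sample part of sensitivity analysis 3 in SAP 5.4.1. Keep that analysis's other condition, which removes anyone treated within 8 weeks whatever the reason.

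The cost is a short SAP amendment and one derived variable, and the samples are already scheduled. The downside is that reported compliance may be slightly lower.

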5.6. Blood Pressure

Blood pressure will be summarized at each visit for the various blood pressure measures: office BP (Screening (Week -8), run-in (Week -2), baseline (Week -1), 4 weeks, 8 weeks, 3 months, 6 months, 1 year and 2 years), 24-hour ABPM (baseline [Week -1], 8 weeks, 6 months and 1 year), daytime ABPM (baseline [Week -1], 8 weeks, 6 months and 1 year) and nighttime ABPM (baseline [Week -1], 8 weeks, 6 months and 1 year). Both systolic and diastolic blood pressure will be presented separately. The mean values at each visit will be presented along with the mean change from baseline (and the matched baseline data for each visit).

The number and percentage of subjects with any decrease from baseline in the various blood pressure measures will be presented. The number and percentage of subjects with any, \geq 5 mmHg, \geq 10 mmHg, and \geq 20 mmHg decreases in blood pressure at each time point will be presented.

Ninety-five percent CIs for the change in mean blood pressure will be computed as well as the 95% CI for the percentage of subjects with any decrease in blood pressure.

These analyses will be conducted in the ITT analysis set.

In order to assess the totality of the data over time, changes in blood pressure at the 8-week, 3-month, 6-month, and 1-year and 2-year (office BP only) visits will be plotted over time by treatment group and assessed via a mixed effects repeated measures model. All available data at the time of analysis will be included in the model. This analysis will be conducted in the ITT analysis set with available data.

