	
in the protocol). After 8 weeks, antihypertensive medications are permitted according to the protocol-defined criteria and proposed titration scheme.
 
Follow-up visits will be performed at 4 weeks, 8 weeks, 3 months, 6 months, 1 year, and 2 years.
 
The study will be unblinded after the last subject has completed the 1-year follow-up visit.
 
Crossover from the Sham Control Arm to the Treatment Arm may be allowed, at the discretion of the treating investigator, after the Data Safety Monitoring Board (DSMB) has reviewed the 1-year data from all subjects and the study has been unblinded.

Study Geography/ Number of Planned Investigational Sites	United States (US) and Europe Multicenter trial with approximately 25 investigational sites (in the US and Europe)
Number of Groups/ Arms/Cohorts	2 groups (Treatment Arm, Sham Control Arm; randomized 1:1)
Number of Targeted Subject Treatment, Total and in Each Arm	Approximately 90 subjects randomized: 
 • 45 subjects in the Treatment Arm • 45 subjects in the Sham Control Arm
Planned Duration of Subject Participation	Approximately 26 months* (for each subject) 
 • Screening period: approximately 4 to 8 weeks • Run-in period: 4 weeks • In-hospital period: 2 days • Follow-up period: 2 years 
*May be different for subjects in Sham Control Arm in the case of crossover: subjects will have a final 1-year follow-up visit after crossover treatment.

INVESTIGATIONAL PRODUCT(S), DOSE AND MODE OF ADMINISTRATION	
Active Product	
Combination Product: Peregrine System Kit
 
Drug Constituent Part: Dehydrated Alcohol Injection, USP
 
Device Constituent Part: Peregrine System Infusion Catheter
 
Dose: 0.6 mL alcohol per treated renal artery. Maximum total dose per subject = 2.4 mL at one treatment session (i.e. during the same procedure).
 
Dosage form: Solution for injection
 
Dosage frequency: Once during the study procedure
 
Mode of administration: Direct infusion to the perivascular space, during an endovascular procedure using the device constituent part

Placebo/Control/ Comparator	
In the Sham Control Arm, only renal angiography will be performed. No alcohol infusion (i.e. no renal denervation) will be performed.
 
Dosage form: Not applicable
 
Dosage frequency: Once during the study procedure
 
Mode of administration: Endovascular

SUBJECT SELECTION

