3.2. Overall Study Design and Plan

This is a Phase 2, prospective, randomized, blinded, sham procedure-controlled, multicenter trial to assess the efficacy and safety of renal denervation by alcohol-mediated neurolysis using the Peregrine Kit. Subjects with a documented history of uncontrolled hypertension who are taking 0, 1, or 2 antihypertensive medications at enrollment will be recruited. Following screening, eligible subjects will enter a 4-week run in period during which they will take no antihypertensive medications.

Subjects who continue to be eligible at the end of the run-in period will be randomized in a 1:1 ratio to one of the following 2 groups via central randomization (stratified by study site):

- Treatment Arm: renal denervation (using the Peregrine Kit) performed with alcohol (0.6 mL per treated renal artery) infused through the Peregrine Catheter (minimum treatment: the 2 main renal arteries [1 per side]; physician is also permitted to treat up to 1 additional accessory artery on each side. Thus, the planned maximum total dose of alcohol is 4 x 0.6 mL = 2.4 mL.)
- Sham Control Arm: only renal angiography will be performed. No renal denervation and no alcohol infusion will be performed.

Subjects will be discharged from the study site the day after the procedure if there are no safety concerns, per the physician's judgment. Subjects with an estimated glomerular filtration rate (eGFR) of >45 and <60 mL/min/1.73 m² will return to provide a blood sample for measurement of serum creatinine 48 to 96 hours after the procedure. Subjects will continue to take no antihypertensive medications during the first 8 weeks after the procedure (except for emergencies, as defined in the protocol). After 8 weeks, antihypertensive medications are permitted according to the protocol-defined criteria and proposed titration scheme.

Follow-up visits will be performed at 4 weeks, 8 weeks, 3 months, 6 months, 1 year, and 2 years, as well as telephone contacts at 2 and 6 weeks in Ireland only.

The study will be unblinded after the last subject has completed the 6-month visit.

Crossover from the Sham Control Arm to the Treatment Arm may be allowed, at the discretion of the treating investigator, after the Data Safety Monitoring Board (DSMB) has reviewed the 6-month data from all subjects, the study has been unblinded, and the subject has completed the 1-year follow-up visit.

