5.7. Antihypertensive Medications

The mean number of antihypertensive medications will be summarized at baseline, 8 weeks, 6 months, 1 year and 2 years. The number and percentage of patients on 0 to 3, and >3 medications will additionally be presented. The mean change from baseline in the number of antihypertensive medications at each visit will be presented along with the matched baseline mean values. Antihypertensive medications will also be summarized by class. These analyses will be conducted in the ITT Analysis Set.

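### Two-year office BP is measured partly before and partly after unblinding, and the SAP analyses the two together without separating them

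*SAP*

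**What the plan says.** **Blinding.** The protocol keeps the subject, the sponsor and the follow-up assessors blinded until one study-wide event. The v7.0 synopsis (Study Design) states: "The study will be unblinded after the last subject has completed the 1-year follow-up visit". Sham subjects may then be offered crossover, after the DSMB has reviewed the 1-year data.

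**The SAP's own rule.** SAP section 2 says the plan is based on Protocol v6.0. Section 3.2 states: "The study will be unblinded after the last subject has completed the 6-month visit". Section 5.2.4 repeats this. Section 3.2 allows crossover after DSMB review of 6-month data, provided the subject has passed the 1-year visit.

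**Two-year efficacy data.** SAP section 3.4.2 lists as a secondary endpoint: "Change in mean office SBP and DBP from baseline to 8 weeks, 6 months, 1 year, and 2 years". Section 5.2.2 adjusts between-group comparisons of BP change for baseline. Section 5.6 says changes at the 8-week, 3-month, "6-month, and 1-year and 2-year (office BP only) visits will be plotted over time by treatment group", and fits a mixed repeated-measures model to all data available at the time. For drugs, section 5.7 says: "The mean number of antihypertensive medications will be summarized at baseline, 8 weeks, 6 months, 1 year and 2 years". Ambulatory BP stops at 1 year.

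**What is not there.** Sections 5.6 and 5.7 and the table list in section 9 make no division by blinding state. Section 5.2.3 treats sham subjects who cross over as withdrawn, with later visits missing. Treatment perception is summarised only at the procedure and at 8 weeks (section 5.14).

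**The concern.** Unblinding falls on one calendar date, but each subject's 2-year visit is counted from that subject's own procedure. Early subjects reach 2 years with allocation still concealed; late subjects reach it when they and their assessors can know the arm. Office BP and drug prescribing are measures that a sham control is meant to protect from such knowledge, and office BP is the only scheduled clinic BP measure at 2 years.

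If the two kinds of visit are reported as one, a change in the arm difference between 1 and 2 years could come from loss of blinding and be read as durability or loss of effect. The crossover rule adds a second difficulty: it removes only sham subjects, and under v7.0 only from the period after unblinding, so the two arms' 2-year data are no longer alike.

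**Working it through.** The documents give no figure for the share of 2-year visits after unblinding, so there is none to reproduce. It can be bounded from the planned dates.

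**Inputs**
- Protocol synopsis, counting months from May 2018 (initiation) as 0: primary endpoint completion June 2021 = 37; study completion March 2023 = 58. Check: 58/12 = 4.8 years, against the stated approximate 5.0.
- Time before a procedure: "Screening period: approximately 4 to 8 weeks" and "Run-in period: 4 weeks", so 8 to 12 weeks. After it: "Follow-up period: 2 years".
- Accrual pattern: not given. Even accrual is assumed, with linear ramps as the range.

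**Accrual length A**
- Last procedure: 37 − 56/30.44 = 35.2 from the 8-week endpoint date, or 58 − 24 = 34.0 from study completion. The two agree to about a month, inside the ±8-week window for the 2-year visit.
- First procedure: 0 to 12 weeks after initiation, so month 0 to 2.8.
- A runs from 34.0 − 2.8 = 31.2 to 35.2 − 0 = 35.2 months.

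**Share after unblinding.** Let w be 24 months minus the last subject's follow-up at unblinding. A 2-year visit falls after unblinding if the procedure took place in the last w months of accrual. With even accrual the share is w/A. With A = 33 and a linear ramp it is 1 − ((A − w)/A)² for rising accrual and (w/A)² for falling accrual.

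| | v7.0 rule (w = 12) | SAP rule (w = 18) |
|---|---|---|
| Even accrual, A = 35.2 to 31.2 | 34% to 38% | 51% to 58% |
| Same, ±8-week visit window | 29% to 44% | 46% to 64% |
| Falling accrual, A = 33 | 13% | 30% |
| Rising accrual, A = 33 | 60% | 79% |

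**One-year visits.** Under v7.0 none falls after unblinding. Under the SAP rule 6/A = 17% to 19% do with even accrual, including 1-year ambulatory BP.

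**Effect of crossover removal** (v7.0, even accrual, A = 33; uptake and a 3-month lag from unblinding to crossover are assumptions). Before removal, 12/33 = 36% of each arm's visits are after unblinding. If every sham subject still awaiting the 2-year visit crosses over, a fraction 3/12 = 0.25 of the sham visits after unblinding remains. The sham share becomes 0.364 × 0.25 / (0.636 + 0.364 × 0.25) = 13%, against 36% in the treatment arm. At 50% uptake it is 26% against 36%.

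**Bias.** If a share p of visits in each arm is after unblinding, and awareness shifts the arm difference in those visits by d, the pooled 2-year difference shifts by p × d. The documents give no value for d, and the formula fails once the arms have unequal shares. No mmHg figure is offered.

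**The case against.** The strongest reply is that little hangs on this. The primary endpoint is at 8 weeks; the protocol's efficacy objective stops at 1 year; the SAP calls secondary analyses supportive and its intervals descriptive; medication endpoints end at 1 year (protocol) or 6 months (SAP), so the 2-year drug count is only a summary. All of this stands and limits the weight of the point.

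Several stronger readings are tempting, and the documents do not support them.
- A reader might infer that a third to a half of the 2-year data is known to be open-label. The share rests on an assumed accrual pattern. Under v7.0 with even accrual the dates support about a third; the half comes only from the conflicting SAP rule.
- A reader might infer that every 2-year visit is pooled. Section 5.2.3 drops the later visits of sham subjects who cross over. That does not cure the problem, because the removal is one-sided.
- A reader might infer that one time trend is forced through blinded and open visits. Section 5.6 does not say whether time is categorical or continuous. If it is categorical, the 2-year estimate need not distort earlier ones. Only the shared plot and model are certain.
- A reader might set an assumed awareness effect against the 5 mmHg that the plan calls clinically meaningful. That figure belongs to the 8-week, off-drug ambulatory endpoint, whereas 2-year office BP follows permitted drug titration.

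Finally, the Randomization and Blinding Plan and the office BP manual are not among the documents. How far assessors learn allocation once the study is unblinded, and how much discretion they have in measuring, cannot be judged. Neither would change the instruction in section 5.6 to analyse the visits together.

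**Conclusion.** The point holds as a limited one. Two-year office BP has mixed blinding status by design, and the SAP neither flags nor separates it. With even accrual over 31 to 35 months, about 34% to 38% of 2-year visits fall after unblinding under v7.0 (13% to 60% with ramped accrual). Under the SAP's 6-month rule it is about 51% to 58%, and some 1-year visits are affected too. These are two conflicting rules, not the ends of one uncertainty range, and they must be reconciled first. All the shares come from planned dates, before any crossover removal.

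Removal of crossed-over sham subjects lowers the sham share only and leaves the arms unlike each other at 2 years. A reader might infer that the efficacy result is compromised. It is not: the 8-week endpoint is untouched, the affected analyses are supportive, and neither the size nor the direction of any awareness bias follows from the documents.

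**What to change.** 1. Reconcile the SAP's unblinding and crossover timing (sections 3.2, 5.2.3 and 5.2.4) with Protocol v7.0.
2. Derive one flag per visit: before or after the actual unblinding date.
3. In sections 5.6 and 5.7 and the matching tables, report 2-year office BP and drug counts by arm and by this flag, labelling visits after unblinding as open-label.
4. Add a version of the mixed model and of the 2-year comparison restricted to visits before unblinding, which under v7.0 are also before crossover. Base any between-arm statement at 2 years on it.
5. The all-data model may stay as a labelled supplementary analysis. Ending the model at 1 year is a possible alternative, but it discards planned data and is not needed.

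The cost is some SAP wording and a date-derived variable. The blinded 2-year comparison would use about 62% to 66% of subjects under even accrual, or roughly 56 to 59 of 90 before drop-out (0.62 × 90 and 0.66 × 90). With the same SD its interval would be about 1.23 to 1.27 times as wide (1/√0.66 and 1/√0.62).
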